Initially, samples will be stored at Arkansas Children's Research Institute. The information collected at the study visit, saliva, blood, urine, stool samples may be stored indefinitely and may be used for future research studies on pediatric nutrition. Prior to the information collected at the study visit and samples being used for future research studies, the PI will assess the ethics and scientific merit of the proposed research with the samples, and proposed future research will be reviewed by the IRB as may be required. The samples and health information collected for the study visit may be shared with researchers at the University of Arkansas for Medical Sciences, Arkansas Children's Hospital, or Arkansas Children's Research Institute. The samples may be shared with an outside group. The samples will only have a study ID number and study acronym to maintain confidentiality. If participants decide they no longer want us to use their samples for future research studies, they may ask the study staff that the sample be removed. If the sample has been shared or if publication of results has occurred, then we may not be able to remove the sample. In addition, research results from the depression scale may be shared with the child's PCP or if the child is actively followed at ACH the depression scale results may be shared with the child's ACH physician if found to be significant and more information may be provided. If the child does not have a PCP or is not actively followed at ACH, then a referral will be made to a PCP for follow-up. For example, a score of 15 or greater on the CES-DC suggests that the participant expresses symptoms of depression. In this scenario, the child's PCP or ACH physician would be notified of the depression scale result. If the child did not have a PCP, then a referral would be made to a PCP near the child's home and the research results from the depression scale would be shared. In addition, the parent would be given information of resources to seek help for the child.

Title: Bioenergetics and Metabolism in Pediatric Populations

PI: [name].

Dissemination of Data

Results of this study may be used for presentations, posters, or publications. The publications will not contain any identifiable information that could be linked to a participant.

References

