mechanisms of insulin resistance, and the development of a non-invasive biomarker in children at an increased risk of developing insulin resistance.

Hypothesis and Specific Aims

We hypothesize that when compared to normal weight or obese insulin sensitive children, obese insulin resistant children will exhibit altered circulating blood cell bioenergetics and a more oxidized plasma redox state and that these alterations will be associated with decreased resting energy expenditure and impaired fatty acid oxidation (FAO). Furthermore, we hypothesize that poor oxidative capacity over time may distinguish between metabolically healthy obese (MHO) and metabolically unhealthy obese (MUO) phenotypes, as well as be predictive of T2D development. We also hypothesize that bioenergetics, REE and FAO will be improved in obese T2D or insulin resistant children after 6 months of metformin therapy that will be prescribed as part of their clinical care. To test these hypotheses, we will evaluate the following Specific Aims:

Specific Aim 1: Determine whether peripheral blood mononuclear cell (PBMC) and platelet bioenergetics (oxidative phosphorylation, glycolysis and fatty acid oxidation) are impaired and whether plasma glutathione-mediated redox/antioxidant capacity is decreased in obese insulin resistant children as compared to normal weight and obese insulin sensitive children.

Specific Aim 2: Determine whether resting energy expenditure (REE) and fatty acid oxidation (FAO) are decreased in obese insulin resistant as compared to lean and obese insulin sensitive children and whether REE and FAO are correlated with bioenergetic and redox profiles.

Specific Aim 3: Determine whether the bioenergetic oxidative capacity measured in circulating cells, PBMCs/platelets, and FAO are valuable predictive markers of T2D in obese children, in addition to distinguishing MUO from MHO subjects.

Specific Aim 4: Determine whether circulating blood cell bioenergetics and whole-body REE and FAO are modulated by metformin therapy that will be prescribed as part of clinical care in

Title: Bioenergetics and Metabolism in Pediatric Populations

PI: [name].

obese children with T2D or insulin resistance.

Study Design and Procedures

This study consists of:

1. An observational cross sectional bioenergetic and metabolic analysis of several groups of children including lean, obese, and T2D.

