2. A longitudinal bioenergetic and metabolic analysis of obese children that will be followed for 12 months, repeated measures will be taken at 12 months post-baseline.
3. A prospective bioenergetic and metabolic analysis of obese insulin resistant children (Aim 3) and newly diagnosed children with T2D or insulin resistance who will be prescribed metformin as part of their clinical care (Aim 4).

A prospective subject and his/her parent will come for the study visit that will last up to 4 hours. A subject (and/or his/her parent) will be asked questions regarding the subject's medical history that will be reviewed by study staff to identify patients who fulfill inclusion/exclusion criteria. In addition, study staff may review medical records from ACH or other healthcare practitioners (such as physicians or pharmacists) outside ACH in order to confirm the inclusion/exclusion criteria. Information from medical records may be collected from the time of consent up until the time that data analysis for this study is complete and results have been published. Study staff will ask parents about demographic information including biologic gender, date of birth, race/ethnicity, and parental occupations as well as grade in school.

Prior to the study visit, study staff may contact the parent and ask for medications that the participant is currently taking and may ask of any new health diagnoses. In the event that the participant is taking medications or has a new health diagnosis that may cause him/her to be ineligible to participate in the study visit, the study visit may be rescheduled or canceled. Study staff may contact a parent and send the IRB approved consent form and information regarding the scheduled visit to the parent(s) prior to the scheduled date. If the consent form has been revised since the last informed consent discussion, the new IRB approved consent form may be sent to parents. If applicable, the parent will be informed of the blood draw and advised that if the parent wishes their child to complete the blood draw at the visit, the child will need to be fasting including no food or liquid after 12 am, except for water and medications the day of the visit.

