1. Intake of Food and Liquid: A parent will be asked by the study staff about the food and drink that the subject eats and drinks the day of and day following the visit (up until the last urine sample is collected for fat oxidation estimation). This is important because the diet will influence the fat oxidation estimation.
2. Anthropometrics: Anthropometric measurements including height, weight, waist circumference, blood pressure, and pulse will be obtained using standardized techniques. BMI-for-age will be calculated and plotted on CDC growth charts to confirm lean/obese stratification.
3. Tanner (Puberty) Stage Assessment: Parents will be asked to complete a form with drawings depicting pubertal development. This form will be used to determine pubertal status. A physician may examine the subject for Tanner Stage (if the parent agrees) during the visit in order to confirm the parental report and for purposes of analyzing study results. The questionnaire given to parents to complete is subjective and a parent could potentially incorrectly assess Tanner Stage. While the inclusion/exclusion criteria prevents the inclusion of those with puberty development, if a parent incorrectly assesses his/her child's Tanner Stage, then this may alter the results or may cause the exclusion of many potential participants based on the parents response, especially in obese participants. Because the results from the samples are reliant on the participants being pre-pubertal with no signs of maturation, conclusions may be incorrectly drawn from the study data if a child has pubertal development. At the beginning stages of puberty, insulin levels rise dramatically showing insulin resistance. Thus, if the study determines the child to have insulin resistance but insulin resistance is actually due to development of puberty instead of being MUO then this

could alter the results and conclusions made from the study. Because of this, it is important to the study and the results to have the correct Tanner Stage level for each participant.

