- Participants in the obese-insulin resistant group may be asked to complete one additional study visits to occur at 12 months (\pm 2 weeks) after the initial study visit. This is to follow changes in bioenergetic and metabolic parameters over time to assess validity and will help establish not only the degree of change in the studied outcomes, but also their predictive value for T2D development, in addition to distinguish between metabolically healthy obese (MHO) and metabolically unhealthy obese (MUO) phenotypes. We may request that all obese insulin resistant participants complete one additional study visit; however, this additional study visit is optional as we do not want to discourage potential enrollment due to the possibility of another visit or lengthy visit. We anticipate roughly 43% of the 70 obese insulin resistant participants will decline a 2nd study visit with a goal of 40 subjects completing a second visit at 12 months (\pm 2 weeks).
- Participants in the newly prescribed metformin group who are prescribed metformin as part of their clinical care will be asked to complete a second study visit to occur six months (\pm 2 weeks) after beginning metformin therapy prescribed as part of their clinical care. We may request that all 20 participants in this group complete the additional study visit; however, the additional study visit is optional as we do not want to discourage potential enrollment due to the possibility of multiple visits or lengthy visits. We anticipate 50% of the 20 participants in this group will decline a 2nd study visit with a goal of 10 subjects completing a 2nd visit at 6 months (\pm 2 weeks).

A participant/parent pair will be compensated \$100.00 in gift cards for each study visit completed. Completion of the study visit may include participation in parental study forms, anthropometric

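### One optional 12-month visit in about 40 children, with no T2D outcome defined, cannot support a conclusion for or against prediction of T2D in Aim 3

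*Combined protocol and SAP*

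**What the plan says.** Under Hypothesis and Specific Aims, the hypothesis is that oxidative capacity over time may distinguish healthy from unhealthy obesity "as well as be predictive of T2D development". Specific Aim 3 is to determine whether blood-cell bioenergetics and fatty acid oxidation "are valuable predictive markers of T2D in obese children". The background section and the description of the additional visits both say that the 12-month repeat will help establish predictive value for T2D.

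Follow-up is described under Study Design and Procedures, where "repeated measures will be taken at 12 months post-baseline". The additional-visit text limits this to the obese insulin-resistant group and makes it optional: "We anticipate roughly 43% of the 70 obese insulin resistant participants will decline a 2nd study visit with a goal of 40 subjects completing" that visit. The Inclusion Criteria make this cohort 5-9 years old and Tanner stage 1.

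The Data Analysis section gives Aim 3 a paired t-test of change in the Aim 1 and Aim 2 outcomes, with a signed-rank test or a mixed model as alternatives. Sample Size Justification bases the 40 children on that t-test. No section defines a T2D outcome, gives an incidence or states an expected number of cases.

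On records, Study Design and Procedures says: "Information from medical records may be collected from the time of consent up until the time that data analysis for this study is complete". The same sentence extends the window to publication of the results. The sentence before it concerns confirming eligibility. No section names records as a source of T2D outcomes.

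**The concern.** A marker can be shown to predict a disease only if some of the children followed develop it. Aim 3 promises prediction of T2D, but the follow-up is one year in about 40 young children, and about 30 of the 70 are expected not to return. The sample size was set for a different question, a mean change.

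Two misreadings are at stake. A significant mean change at 12 months could be presented as bearing on T2D prediction, which it does not. Alternatively, the absence of any visible link with T2D could be taken to mean that the markers do not predict it, when there were few or no cases to predict. Either would mislead the decision that the plan says these data should inform, namely whether a larger study is warranted.

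**Working it through.** **Inputs from the documents.** Goal of 40 children at 12 months out of 70 (additional-visit text); paired t-test, 80% power, alpha 0.05, detectable d = 0.45 (Sample Size Justification); groups ii and iii of 20 and 70 obese children (Study Population).

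**Input not in the documents.** T2D incidence. Annual risks from 0.5% to 5% are assumed, with 10% as an extreme.

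**1. The plan's own figure.** The exact noncentral-t calculation for a paired t-test (39 degrees of freedom, two-sided 0.05, 80% power) gives a detectable d of 0.454, and power at d = 0.45 is 79.3%. The stated 0.45 reproduces. It concerns mean change and says nothing about T2D.

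**2. Expected cases at 12 months.** Expected cases = 40 × risk; chance of none = (1 − risk)^40.

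| Assumed annual risk | Expected cases in 40 | Chance of no case |
|---|---|---|
| 0.5% | 0.2 | 82% |
| 1% | 0.4 | 67% |
| 2% | 0.8 | 45% |
| 5% | 2.0 | 13% |
| 10% | 4.0 | 1.5% |

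**3. Cases needed.** For a continuous marker, the cases needed for 80% power at two-sided 0.05 are (1.96 + 0.84)² / (ln HR)², where HR is the hazard ratio per standard deviation.

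- HR 2.0: about 16.3 cases, a one-year risk of 16.3/40 = 41%.
- HR 2.5: about 9.3 cases, or 9.3/40 = 23%.
- HR 3.0: about 6.5 cases, or 6.5/40 = 16%.

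**4. Precision with few cases.** With 2 cases among 40 and a true AUC of 0.75, the Hanley-McNeil standard error is 0.205, so the 95% half-width is 1.96 × 0.205 = 0.40. With no case in 40, the exact two-sided 95% upper limit for the one-year risk is 1 − 0.025^(1/40) = 8.8%.

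**5. What a record check could add.** Covering all 70 insulin-resistant children gives 70/40 = 1.75 times as many children as the visit. Adding the 20 healthy obese gives 90/40 = 2.25, and expected cases rise by that factor only if their risk is the same. Cumulative cases = n × [1 − (1 − risk)^years], assuming constant risk and complete records:

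| Assumed annual risk | 70 children, 3 years | 70 children, 5 years | 90 children, 5 years |
|---|---|---|---|
| 0.5% | 1.0 | 1.7 | 2.2 |
| 1% | 2.1 | 3.4 | 4.4 |
| 2% | 4.1 | 6.7 | 8.7 |
| 5% | 10.0 | 15.8 | 20.4 |

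Only at the top of the range, after about five years of complete records, does the count reach the region of 16 needed for HR 2.0. The protocol's record window has no fixed length, so the 3 and 5 years are illustrations.

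**The case against.** The strongest defence is that the wording is hedged. The background and the additional-visit text say the repeat will help establish predictive value, the hypothesis is phrased as a possibility, and the sample size text treats the results as a guide to a larger study. That stands as to tone. Aim 3 itself, however, is worded as a determination and is not labelled exploratory.

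A second defence is that no prediction analysis is planned, so no negative prediction result would be produced. That is correct, and it confirms that the aim has no analysis behind it.

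Four stronger readings are tempting, and the documents do not support them:

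- *That nothing collected at the visits could reveal T2D.* Fasting insulin and glucose are listed among the blood analyses, additional visits repeat the initial procedures, and staff may ask about new diagnoses beforehand. What is missing is a T2D outcome defined from these data.
- *That record access is confined to eligibility, so children who decline the visit can have no outcome.* The sentence opening the window states no purpose limit. Records are simply not named as a T2D source.
- *That the protocol itself says these children are too young to develop T2D within the year.* The sentence "At the beginning stages of puberty, insulin levels rise dramatically showing insulin resistance" appears in the Tanner stage item, which is about parents misreporting stage and so confounding classification. It does not describe how T2D develops, and no age of puberty onset is given. The case-count argument does not need it.
- *That a record check would rescue the aim.* At 1% a year, five years of complete records on 70 children give about 3.4 cases.

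**Conclusion.** The point holds. As designed, the study cannot support a conclusion for or against prediction of T2D. At any assumed annual risk up to 5%, the 12-month visit yields at most 2 expected cases. Even 10% gives 4, against about 16 needed for a hazard ratio of 2.0 per standard deviation and 6.5 for 3.0.

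The incidence is an assumption, but the conclusion is not sensitive to it: a one-year risk of about 16% would be needed before even a hazard ratio of 3.0 could be tested in 40 children. The arithmetic also assumes that the goal of 40 is met and that every case in those children is found, both of which favour the plan.

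The mean-change analysis is unaffected, and its stated effect size is right. This point does not address the part of Aim 3 that separates healthy from unhealthy obesity.

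**What to change.** 1. In the background, in Hypothesis and Specific Aims, and in the additional-visit text, limit the 12-month conclusion to change in the metabolic and bioenergetic measures taken at both visits. State that T2D prediction is exploratory, will be reported as a case count with an exact interval, and will not be read as evidence of no predictive value.
2. In Study Design and Procedures and the additional-visit text, name the permitted record window as a T2D outcome source. At data lock, check the available records of every obese child in groups ii and iii, returned or not, for a dated T2D diagnosis. Report by group as time from baseline. Confirm first that consent covers this use, and exclude information dated after withdrawal, since Data Handling and Recordkeeping rules out collecting it.
3. Record starts of glucose-lowering treatment separately and do not count them as T2D without a diagnosis. Study Population and the Inclusion Criteria show that metformin is also prescribed for insulin resistance, so counting starts would add children without T2D to the case count.

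The cost is a more modest claim about T2D, revised wording, and staff time for one record check per obese child (90 at the target numbers). Records outside the hospital may be incomplete. The gain is 1.75 to 2.25 times as many children per year of follow-up. That is worth having for the case count, but it is unlikely to be enough to test prediction.
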